2.2. Study objectives

Primary Objective: The primary objective of this study is **to quantify the change** in HIV program performance among health facilities with Project Unlocked interns in programmatic roles (intervention sites) versus health facilities where Project Unlocked interns are not in programmatic roles (control sites) by examining the difference in programmatic indicators related to **90-90-90 targets**.

- **HIV testing (90)**: Percentage of individuals who received HIV testing services (HTS) and received their results, among all persons who were seen at the facility.
- **Linkage to treatment (90-90)**: Percentage of individuals testing positive who were linked to treatment at the facility (same day of testing and by 14 days post-testing).
- **Retention in care (90-90-90):** Percentage of people on treatment for HIV who default from treatment. This measure will be used as a proxy for viral suppression, which is the "third 90" of the 90-90-90 targets.

Analyzing the 90-90-90 targets is the primary objective for this study, as the interns in programmatic roles are performing activities directly linked to these indicators, i.e., testing, linkage to care, and retention in care (see Figure 1). As such, we have reason to believe interns could **directly impact performance**, as measured by these indicators.

Secondary Objective: We will measure how the presence of interns at health facilities **indirectly** impacts other HIV services that are not directly part of the programmatic interns' work responsibilities, such as initiation and completion of isoniazid preventive therapy (IPT) among people newly diagnosed with HIV. The indicators used to measure the secondary objectives will also be those routinely reported (i.e., through DHIS and TIER.Net).

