3.4. Randomization of study clinics

All facilities that are eligible and willing to participate in this study (18-24 facilities) will be randomized to the control or intervention arm. We will use stratification improve similarity between facilities in the treatment and control groups. Facilities will be, at minimum, stratified by HIV programmatic performance (measured by HIV testing) and, if necessary, also stratified by size (measured by total monthly head count at the facility). The final decisions for stratification will be driven by the facility data observed in the year proceeding the study. The minimal proposed stratification is outlined in Figure 2.

We will randomize an equal number of facilities to the control or intervention group within each strata using a random number generator. We will randomly assign facilities at a joint meeting between study implementors and program staff (e.g., the NMM health district manager).

[figure not shown]

Figure 2. Allocation of facilities to control or intervention

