6.2. Data management

Monthly facility-level data for 10 months (baseline through 9 months) of key indicators along with facility-level characteristics at baseline (i.e., sub-district, facility size, treatment group), will be collated into a CSV file. Data will be abstracted from the routinely reported monthly, Excel-based reports into this dataset. After all data have been merged, the baseline dataset will be frozen and designated members of the study team will conduct data cleaning in R.

Structure of Dataset

The dataset will include one sheet and be in wide format (i.e., one row per facility). There will be one column per indicator of interest per month. There will be one row per facility, to enable easy aggregation of data collected per facility from months 4-9 of the intervention period. Data will be cleaned and organized in R.

Data entry validation

All data entry will be conducted under routine programmatic conditions. Program staff will use routine, existing facility-level protocols to enter and submit their data to Aurum and other entities. This study will not propose variations on this routine process (i.e., there is no data entry validation specific to this study). While one study member will collate the dataset from monthly reports, a secondary member will review the dataset to ensure quality of the final dataset. The dataset will be collated after the intervention period (i.e., at month 9). This will ensure that the most up-to-date data are captured in our analysis, and that the study team does not use the data to prospectively alter performance of the intervention.

Data cleaning

Study staff will review the routinely reported data for outliers and send inquiry to program staff on any outliers. Study staff will adjust any outliers in consultation with the facilities that generated the data.

Access to dataset

The dataset will be password protected and shared only with study and program staff.

Locking of database

The dataset will be cleaned in a standard statistical program (e.g., STATA or R). The dataset will be locked after all data have been merged and reviewed for outliers.

Information security

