HIV, % linked to treatment, and % retained in care in each facility for the six months of the intervention period. We will calculate this by aggregating each indicator, then calculating the outcomes of interest (percentages) based on the six-month total counts. In the second step, we will carry out weighted 2-sample t-tests to test the null hypothesis that there is no significant difference between the intervention and the control groups with respect to these summary measures. Weighted approaches are preferred here, as they have been shown to improve efficiency when clusters are not of the same size [24], which is the case in our trial. In our approach, the weights are set to be the inverse of the estimated variance of the cluster summary measures, that is,

$$w_i = \frac{1}{v_i + \sigma^2}$$

where v_i is the variance of the cluster level summary for facility i and σ^2 is the between-cluster (between-facility) variance. We will also conduct additional analyses adjusting for facility-level factors as necessary.

Should changes in testing, linkage to care, and retention in treatment be noted in the analysis, we will descriptively examine these indicators by sex and age groups of interest to understand what demographic was receiving additional testing and/or care as a result of this program. These indicators are available in aggregate in the routinely reported data.

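### The primary t-test uses neither the randomisation stratum nor each indicator's baseline value; it is unbiased, but gives up precision if facility performance persists over time

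*Protocol*

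**What the plan says.** Randomisation (Protocol 3.4): "Facilities will be, at minimum, stratified by HIV programmatic performance (measured by HIV testing"), with facility size added if needed. Allocation is balanced inside strata: "We will randomize an equal number of facilities to the control or intervention group within each strata".

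Data (Protocol 6.2): the dataset holds "Monthly facility-level data for 10 months (baseline through 9 months") of the key indicators. Section 5.1 and the statistical analyses text in section 7.1 restrict the outcome analysis to months 4-9.

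Test (Protocol 7.1, statistical analyses): each facility gets one percentage per outcome from its six-month totals, and then "we will carry out weighted 2-sample t-tests to test the null hypothesis" of no difference between arms. On weighting, "the weights are set to be the inverse of the estimated variance of the cluster summary measures", that is w = 1/(v + σ²). No stratum or baseline term appears. The only mention of adjustment is: "We will also conduct additional analyses adjusting for facility-level factors as necessary".

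**The concern.** Stratifying on a variable that predicts the outcome balances that variable across arms, so the true sampling error of the arm difference shrinks. A two-sample t-test does not see this. It leaves the between-stratum variation in its error term, so its interval is wider than it needs to be and its type I error falls below the nominal level. Leaving out the baseline value of the outcome forgoes further precision. The weights do not help here, because they deal with unequal precision of the facility percentages and not with explained differences between facilities.

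This matters because the trial has only 9-12 facilities per arm. Section 7.1 says the number is set by how many eligible clinics exist, and section 8 accepts the small size as unavoidable. Efficiency of analysis is one of the few ways left to gain power.

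**Working it through.** **1. The plan's own figure.** Inputs from section 7.1 and Table 4: control proportion 0.14, cluster size m = 1,687, cv = 0.596 (taken as the cv of cluster size), 80% power, 5% level (two-sided assumed).
- Design effect = 1 + ((1 + cv²)m − 1) × ICC. At ICC 0.01: 1 + ((1 + 0.355) × 1,687 − 1) × 0.01 ≈ 23.9. At ICC 0.03 it is 69.6, and at 0.05 it is 115.3.
- Effective n per arm = (clusters × m) / design effect, solved for the intervention proportion.
- Result at ICC 0.01 / 0.03 / 0.05: 0.190 / 0.230 / 0.259 with 12 per arm and 0.199 / 0.245 / 0.280 with 9. Table 4 gives 0.19 / 0.23 / 0.26 and 0.20 / 0.25 / 0.28, so it reproduces. It takes no credit for strata or baseline.

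**2. The same formula with baseline credit.** Multiply the between-facility variance by (1 − r²). With 12 per arm and ICC 0.03, the detectable proportion moves from 0.230 (r=0) to 0.217 (r=0.5) and 0.203 (r=0.7).

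**3. What the strata capture.** In Table 1, 30 facilities have a readable head count. Tested divided by head count has mean 0.117, SD 0.042 and range 0.02 to 0.21. The share of baseline variance explained by strata on that proportion is:

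| Indicator | Two strata | Three strata |
|---|---|---|
| % tested | 65% | 80% |
| Early default / total on ART | 6% | 7% |
| Same-day initiation / newly positive | 3% | 9% |

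The strata argument is therefore about % tested. For the other two outcomes only their own baseline could help.

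**4. Simulation for % tested.** Twenty-four facilities are drawn from the 30, split into two strata on testing rate and allocated 1:1 within stratum. Follow-up has correlation r with baseline. The planned t-test is compared with a regression on arm, stratum and baseline. Equal weights are a fair stand-in for the planned ones: with about 12,000 visits per facility in six months, the sampling variance is about 0.117 × 0.883 / 12,000 ≈ 0.00001, against a between-facility variance of 0.042² ≈ 0.0017.

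| r (assumed) | Type I error, planned test | Power for 5 points, planned | Power for 5 points, adjusted |
|---|---|---|---|
| 0 | about 5% | 80% | about 78% |
| 0.3 | just under 5% | 80% | 81% |
| 0.5 | 3.5% | 82% | 89% |
| 0.7 | 1.7% | 83% | 96% |

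Five points is the smallest difference in Table 4 (0.14 to 0.19). At r=0.7 the mean half-width of the confidence interval is 3.5 points for the planned test and 2.6 points adjusted.

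**5. Closed-form check.** Detectable difference = (t.975 + t.80) × SD × √(1 − r²) × √(2/12). With 22 degrees of freedom, (2.07 + 0.86) × 0.0418 × 0.408 = 5.0 points at r=0. Multiplying by √(1 − r²) gives 4.3 points at r=0.5 and 3.6 at r=0.7.

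**The case against.** The strongest reply is that nothing here is invalid. An unadjusted comparison of cluster summaries after stratified randomisation is unbiased, and its error rate stays at or below 5%. That stands: the point concerns efficiency. The gain also rests on r, which the protocol does not give, and adjustment costs a little power if r is near zero. That stands too.

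A reader might infer more from the text in four places.
- **That the plan contradicts its objective.** Section 2.2 sets out "to quantify the change" in programme performance, but goes on to define this as a between-arm difference in indicators. A follow-up comparison of randomised arms answers that.
- **That Table 1 shows stable differences between facilities.** It gives one average or snapshot per facility and cannot show persistence. The extremes of same-day initiation (0% and 100%) come from rounded monthly means such as 0 of 4 and 1 of 1.
- **That the strata make the test conservative for all three outcomes.** Step 3 of the working shows they barely explain same-day initiation or early default.
- **That covariates will be picked after the results are seen.** The adjusted analyses are indeed undefined in the protocol, but a statistical analysis plan commonly names the covariates, and one may exist. The document does not support the inference.

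**Conclusion.** The protocol fixes a primary test that leaves out its own stratification factor and the baseline data it already plans to collect. The consequence is lost precision, not bias or false positives. For % tested with 24 facilities, power for 5 points would be about 7 percentage points higher with adjustment at r=0.5 (82% to 89%) and 13 higher at r=0.7 (83% to 96%). The gain is negligible at r=0.3, and about 2.5 points are lost at r=0. These figures assume two strata, near-equal weights and facility variation like that in Table 1. For linkage and default no size can be given from the documents; any gain depends on how well each indicator's own baseline predicts its follow-up. This is a worthwhile, low-cost improvement, not a correction of an invalid analysis.

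**What to change.** Before any outcome data are seen, make the primary analysis a facility-level linear regression of the months 4-9 summary on arm, randomisation stratum and that facility's pre-trial value of the same indicator. Keep the planned inverse-variance weights, which matter more for linkage, where there are about 50 positives per facility in six months and very unequal counts. Use t inference on the number of facilities minus the number of parameters. Keep the unadjusted weighted t-test as a sensitivity analysis.

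Where one month's counts are small, take the baseline from several pre-trial months of the same routine reports. This applies to linkage: new positives average about 8 per facility per month and range from 1 to 23.

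Cost: about two degrees of freedom out of 16-22 (22 to 20 with 24 facilities, 16 to 14 with 18), and more if size strata are added. There is a slight loss of power if baseline does not predict the outcome. Some extra abstraction is needed, because the planned dataset starts at month 0 and Table 1 has no 14-day initiation or late default and gives early default for July 2019 only. No new primary data are required.

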5. STUDY OUTCOME

5.1. Primary Outcomes

There are three primary outcomes of interest in this study, which will be assessed for a total of **six months** through a combination of variables that reported monthly through TIER.net to Aurum. The indicators that will be used to assess the primary outcomes of interest are summarized in Table 3 below.

First Outcome: % **Tested for HIV** –Number of individuals who received HIV testing services (HTS) and received their results out of all individuals visiting the clinic for services. This will be calculated through use of two standard indicators.

• % Tested for HIV = HTS_TST / Head Count

Second Outcome: % **Linked to Treatment** – *Number of individuals testing positive who were linked to treatment at the facility, out of all individuals who tested positive for HIV.* There will be two measures we examine:

- % Linked to care on day of testing = Initiated Same Day / HTS TST Pos
- % Linked to care within 14 days of testing = Initiated 14 Days / HTS_TST_Pos

Third Outcome: % **Retained in care** –*Number and percentage of people on treatment for HIV who default from treatment (early default, late default).* There will be two measures we examine:

- % Early Default = ART Default Early / Total on Treatment
- % Default = ART Default Late / Total on Treatment

We will rely on indicators reported through routine reporting mechanisms, primarily relying on TIER.Net due to its monthly frequency of reporting and the high number of indicators included in these reports. The numerators and denominators for each indicator will come from the same reporting period (i.e., the same month).

While the full study is nine months in duration, the first three months will be a "run in" period, data from which will not be used to assess study outcomes. We will use data from months 4-9 (i.e., six months of data) of the intervention period to calculate these outcome measures.

Table 3. Indicators that will be used to measure outcomes of interest are reported monthly through TIER.Net.

Outcome	Indicator	Indicator Definition			
% Tested for HIV	Head Count	Number of individuals visiting the clinic for services			
	HTS_TST	Number of individuals who were tested for HIV			
% Linked to	HTS_TST_POS	lumber of individuals who tested positive for HIV			
Treatment	Initiated Same Day	Number of individuals who were started on ART on the same day they tested positive for HIV			

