7. STATISTICAL CONSIDERATIONS

7.1. Sample size estimation

Sample size: We will enroll 18-24 clinics in this study, resulting in 9-12 clinics being in the treatment and the control arms of the study. The sample size is pre-determined by the number of available eligible clinics.

Study power: In Table 4 below, we show the minimum detectable differences in HIV testing that can be detected with 80% power under different assumptions of the intra class correlation (ICC) (0.01-0.05), at 5% level of significance, and for different cluster size (number of facilities). For example, if there are 24 facilities in this study (12 in each of the study arms), we will have 80% power to detect a difference of at least 35% in HIV testing when the ICC is 0.01, and at 5% level of significance. Similarly, if we have 18 facilities in this study (9 in each of the study arms), we will have 80% power to detect a difference in HIV testing of at least 45% when the ICC is 0.01, and at 5% level of significance.

These power calculations are based on data on the eligible facilities from the NMM district that show there was an average of 1,687 people tested for HIV in six months per clinic and that average HIV testing was at 14% in this time period.

Significance level	Power	Current proportion of total headcount tested for HIV	Number of clusters	Average cluster size	Coefficient of variation (cv)	ICC	Proportion of headcount tested for HIV needed to achieve 80% power
5% 80%						0.01	0.19
	0.14	12	1687	0.596	0.03	0.23	
						0.05	0.26
5%	80%	0.14	9	1687	0.596	0.01	0.20
						0.03	0.25
						0.05	0.28

Table 4. Assumptions for power calculations, with estimated HIV testing level needed to achieve 80% power.

Statistical analyses

The first three months of the study comprise the "run in" period. Data from the wash-out period will not be used in the analysis. We will use six months of facility data collected during months 4-9 of the intervention for this analysis.

We will employ 'Cluster-level' methods to conduct statistical analysis in a two-stage approach here. The first step will consist of estimating a summary measure for each cluster (facility): we will calculate the % tested for

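### The weight formula leaves open the usual own-proportion variance, which lets a facility's result set its own weight and can push the 14-day linkage test off its 5% level

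*Protocol*

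**What the plan says.** Protocol section 7.1, under Statistical analyses, sets a two-stage analysis. Each facility's counts over months 4–9 are totalled and turned into percentages, and the arms are then compared by weighted two-sample t-tests. The stated reason for weighting is that facilities differ in size. The weight is w_i = 1/(v_i + σ²): "the weights are set to be the inverse of the estimated variance of the cluster summary measures", where v_i "is the variance of the cluster level summary for facility i" and σ² is the between-facility variance. No estimator is given for either term, and nothing is said about percentages at 0%, at 100% or above 100%.

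The formula applies to all primary outcomes, including two linkage measures (section 5.1): same-day initiations over positives, and initiations within 14 days over positives. Section 5.1 adds that "The numerators and denominators for each indicator will come from the same reporting period", meaning the same month. The trial is small, "resulting in 9-12 clinics being in the treatment and the control arms of the study".

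**The concern.** For a percentage, most analysts would compute v_i as p_i(1 − p_i)/n_i. That quantity reflects more than size. A facility that happens to link everyone gets v_i = 0 and the maximum weight 1/σ², however few patients it has. Weight and outcome are then correlated, and the t-test's reference distribution no longer applies.

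Linkage is where this can matter. Table 1 shows 1 to 23 new positives per facility per month, so about 6 to 138 over six months. In the 14-day measure, numerator and denominator are separate counts from the same month, so someone who tests late in one month and starts treatment early in the next adds to the later month's numerator only. A ratio above 100% is therefore possible, and v_i then turns negative. Linkage is one of three primary outcomes, and with 9–12 facilities per arm a single distorted weight counts.

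**Working it through.** **The plan's own figures.** Table 4 covers HIV testing only. The inputs are 9 or 12 facilities per arm, cluster size 1,687, cv 0.596, baseline 0.14 and a two-sided 5% level (sidedness assumed). With design effect 1 + ((cv² + 1)m − 1) × ICC, all six cells reproduce: 0.1905, 0.2300, 0.2591 for 12 per arm and 0.1989, 0.2455, 0.2800 for 9. The protocol gives no comparable figure for linkage or for the weights.

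**HIV testing.** With p = 0.14 and n = 1,687, v = 0.14 × 0.86/1,687 = 0.00007. At the lowest ICC in Table 4, σ² = 0.01 × 0.14 × 0.86 = 0.0012. σ² dominates, so the choice of v_i hardly matters.

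**Same-day linkage, from Table 1.** Take p_i = same-day initiations/new positives and n_i = 6 × monthly positives, using rounded monthly averages.
- Two facilities are at 0% and two at 100%, out of 31. None exceeds 100%.
- The mean is 0.515, the mean own-variance v_i is 0.0046, and σ² is 0.060 after removing it.
- The largest weight is 1.21 times the smallest, the correlation of weight with positives is +0.43, and a 0% or 100% facility gets 1.07 times the mean weight.
- Simulated type I error is 5.4–5.9% at this spread (SD 0.245), and 5.6–7.4% if the SD is assumed to be 0.05–0.15.

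**How the mechanism acts on 14-day linkage.** Illustration with assumed mean 0.90 and SD 0.03, so σ² = 0.0009:
- 24 of 24 linked: v = 0, w = 1/0.0009 = 1,111.
- 21 of 24 linked: v = 0.875 × 0.125/24 = 0.00456, w = 1/0.00546 = 183.
- 76 of 84 linked: v = 0.905 × 0.095/84 = 0.00103, w = 1/0.00193 = 519.

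Two facilities of equal size differ sixfold in weight because of three patients, and the small one at 100% outweighs one 3.5 times its size. With pooled p = 0.90, both facilities of 24 get 1/(0.09/24 + 0.0009) = 215, and the facility of 84 gets 1/(0.09/84 + 0.0009) = 507.

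**Type I error for 14-day linkage.** Null simulation, 6,000 runs per setting; facility sizes from Table 1 positives × 6; σ² by moments with a floor of 0.0001; no ratio above 100%. The means and SDs are assumptions. Each cell gives 9 per arm; 12 per arm.

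| Mean/SD | Own v_i | Pooled v_i | Equal weights |
|---|---|---|---|
| 0.80/0.05 | 8.0; 8.7% | 5.7; 6.1% | 4.9; 5.5% |
| 0.85/0.05 | 8.0; 9.6% | 5.4; 5.9% | 5.0; 5.4% |
| 0.85/0.10 | 4.6; 5.2% | 5.0; 5.4% | 4.6; 5.2% |
| 0.90/0.03 | 16.4; 16.5% | 5.4; 4.9% | 5.3; 4.4% |
| 0.90/0.05 | 8.6; 7.2% | 5.1; 5.1% | 5.3; 4.6% |
| 0.95/0.02 | 10.9; 8.6% | 5.2; 5.2% | 4.2; 4.7% |
| 0.95/0.05 | 2.5; 2.3% | 5.1; 4.8% | 4.9; 4.8% |

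A second simulation, with a far smaller floor on the variance, gave 3.5; 3.2% at 0.90/0.10 and 7.6; 4.9% at 0.95/0.03 with own v_i. The direction of the error therefore depends on mean and spread together. At means of 0.90 or more, the top weight fell on a facility of median size or smaller in 69–86% of runs.

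**Ratios above 100%.** In Table 1, initiations exceed new positives in 13 of 31 facilities. That column counts all initiations, so it shows only that same-month ratios can pass 100%. Putting it into the formula, 6 initiated over 3 positive gives v = 2 × (−1)/18 = −0.111, and 2 over 1 gives 2 × (−1)/6 = −0.333. With σ² = 0.06 the sums are −0.051 and −0.273, so both weights are negative. If 2–4% carry-over is assumed for the 14-day measure and the formula is used literally with only a tiny floor, 12–62% of null runs reject. Setting negative v_i to zero brings this to 3.6–7.9%.

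**The case against.** The strongest reply is that the protocol never states p_i(1 − p_i)/n_i. A pooled v_i fits its wording, holds the level, and may be specified in an analysis plan that is not shown. The first two parts are correct. But the protocol chose to print the formula and to define v_i as the variance of the individual facility's summary. The more obvious reading can fail and nothing requires the safer one, so the text needs tightening where it stands.

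The second reply is that the 14-day rates are invented. That also stands: the only linkage spread in the protocol, for same-day initiation, is wide (SD about 0.245), and at 0.85/0.10 the own-variance test is close to 5%. The inflation is conditional.

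A reader might also infer more than the documents support:
- That the smallest clinics always get the largest weights. On Table 1 same-day figures, larger clinics tend to get slightly more, since σ² caps every weight. The reverse is a tendency at high linkage.
- That both linkage tests lose their level. Same-day linkage stays near 5% at the Table 1 spread, and by definition its ratio cannot pass 100%.
- That error rates above 20% are to be expected. In these simulations that needed ratios above 100% and uncorrected use of the formula.

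**Conclusion.** The point holds for the 14-day linkage measure, conditionally. If v_i is computed from each facility's own proportion, the nominal 5% test rejects in about 7–17% of null simulations in most of the settings tried with high linkage and modest spread (means 80–95%, SD 0.02–0.05). It is not inflated everywhere in that range: it is near nominal to mildly inflated at 0.95/0.03 and conservative at 0.95/0.05 (2–3%), as it also is at 0.90/0.10 (3–4%). Pooled or equal weights stay at about 4–6% in every setting. The results rest on assumed 14-day rates, Table 1 volumes, a two-sided test and a moment estimate of σ². HIV testing and same-day linkage are little affected. The plan should be changed, because the remedy costs almost nothing and the outcome is primary.

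**What to change.** In section 7.1, define v_i = p(1 − p)/n_i, with p the overall pooled proportion across both arms, so that weights depend only on facility size, which is the protocol's stated reason for weighting. Add that equal weights are used if the estimated σ² is zero or if the pooled p is at or above 1.

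Restricting the linkage numerator to people who tested positive in months 4–9 would keep the ratio below 100%, but it needs person-level linkage of tests to initiations. Sections 3.6 and 6.1 allow only aggregate facility counts, so it is not proposed here.

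Cost: one sentence in the plan and a negligible loss of efficiency. No change to data collection or sample size.
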